#### 9.2 Setting

The overall source cohort will consist of all individuals aged 18 years or older as of the country-specific start dates.

The main cohort (i.e., the general population cohort) for objective #1-3 and #5-8 will consist of individuals who:

- 1) Are aged ≥50 years in Denmark and Sweden, ≥60 in Finland, and ≥65 in Norway (country-specific age cut-off for booster recommendations)
- 2) Have a known residency within the specific country
- 3) Have received AZD1222, BNT162b2, or mRNA-1273 vaccines only (AZD1222 as part of the primary vaccination course only)
- 4) Did not receive a booster (i.e., the third or fourth vaccine dose) within 90 days after the last received vaccine dose
- 5) Did not receive the fourth dose before the country-specific start dates (as this would indicate individuals who were particularly vulnerable to severe disease or individuals with immunocompromising conditions and thus would not be representative of the target general population)
- 6) No history of Covid-19 hospitalization prior to the country-specific start dates

Objective #3 will be evaluated in secondary cohorts consisting of individuals hospitalized for Covid-19 from the main cohort.

Objective #4 will be evaluated in secondary cohorts consisting of presumed immunocompromised individuals aged  $\geq$ 18 years. Immunocompromised will be defined as fulfilling at least 1 of the conditions in the table below:

Immunocompromised condition	Definition
Solid malignancy (1)	ICD-10 codes: C00–C80 (except C44) registered within 3 years
	prior to the index date

Hematologic malignancy (2)	ICD-10 codes: C81-C86, C88, C90-C96, D46, D47, D61.0, D70.0,
	D61.2, D61.9, D71 registered within 3 years prior to the index
	date
Rheumatologic or inflammatory disorder (3)	ICD-10 codes: D86, E85 [except E85.0], G35, J67.9, L40.1, L40.5,
	L93, L94, M05-M08, M30, M31.3, M31.5, M32-M35, M46
	registered within 3 years prior to the index date
Other intrinsic immune condition or	ICD-10 codes: B20, B21, B22, B231, B232, B24, B9735, D27.9,
immunodeficiency a (4)	D61, D72.8, D80, D81 [except D81.3], D82-D84, D89 [except
	D89.2], K70.3, K70.4, K72, K74.3-K74.6 [except K74.60 and
	K74.69], N04, 0987, R18, Z21, Z992 registered within 3 years
	prior to the index date
Organ or stem cell transplant (5)	ICD-10 codes: T86 [except T86.82-T86.84, T86.89, and T86.9],
	Z94, and Z98.85 registered within 3 years prior to the index date

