#### **Covariates**

For our main cohort analysis objective #1-2 and #5-8, we will take the following potential confounders into account: age (using birth cohort), sex, region of residency, calendar time of last mutual vaccine dose (i.e., either third or fourth dose depending on boosted vs unboosted- [i.e., 4 vs 3-] or between boosters- [i.e., 4 vs 4-] analyses), vaccination priority group (nursing home residents, healthcare personnel, at risk of severe Covid-19 due to comorbidities), previous SARS-CoV-2 infection and selected comorbidities. For the Covid-19 hospitalised cohort analysis (objective #3), we will also include length of hospitalisation as a covariate (as a proxy for severity of event) but not use previous SARS-CoV-2 infection history (as per eligibility criteria, all included are SARS-CoV-2 infected [as hospitalised due to this infection] and any previous SARS-CoV-2 infection is most likely not a strong confounder within the comparison). For the immunocompromised cohort analysis (objective #4), we will also include subtype of immunocompromised condition (as categorized in the 6 levels in the table above). In addition, we will assess the data distribution to help find the optimal categorization of the variables "Time since SARS-CoV-2 infection", "Time between primary course and first booster", and "Time between first and second booster". Further details of covariate definitions are provided in table below.

Variable	Country	Data source and details	Values/codes
Ago	Denmark	The Civil Registration System. Recorded birth year. Age defined as the country-specific start date minus birth year.	Categorical (for adjustment, using birth year): 5-year bins
Age	Finland	The Finnish Population Information System. Recorded birth year. Age defined as the country-specific start date minus birth year.	Binary (for stratification): ≥ 70 years</td

Variable	Country	Data source and details	Values/codes	
	Norway	Norwegian Population Register. Recorded birth year. Age defined as the country-specific start date minus birth year.		
Sweden		The Total Population Register. Recorded birth year. Age defined as the country-specific start date minus birth year.		
	Denmark	The Civil Registration System. Defined as registered sex.		
Sex	Finland	The Finnish Population Information System. Defined as registered sex.	Binary: male, female	
Jex	Norway	Norwegian Population Register. Defined as registered sex.	billary. maie, lemaie	

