	Norway	Norwegian Patient Register. Defined as any recorded ICD-10 diagnosis during inpatient or outpatient contact in hospital or from private-practicing specialists and before first Covid-19 vaccination (look-back 3 years).	Binary: yes/no (ICD-10 codes: E10- E14, I05-I09, I110, I130, I132, I1420, I20-I23, I25-I28, I33-I39, I426-I429, I48, I50)	
	Sweden	National Patient Register. Defined as any recorded ICD-10 diagnosis during inpatient or outpatient contact and before first Covid-19 vaccination (look-back 3 years).  Swedish Prescribed Drug Register. Antidiabetic drugs use defined as ≥2 filled prescriptions during 2020.	Binary: yes/no (ICD-10 codes: E10- E14, I05-I09, I110, I20-I28, I34-I37, I39, I42, I43, I46, I48-I50; ATC code: A10)	
Comorbidity 3: Autoimmunity- related conditions c	Denmark	The National Patient Register. Defined as primary diagnoses regardless of type of hospital contact registered before the start date for the country-specific rollout of the fourth vaccine dose (look-back 3 years).	Binary: yes/no (ICD-10 codes: D510, D590, D591, D690, D693, D86, E050, E063, E271, E272, G122G, G35, G610, G700, I00, I01, K50, K51, K743, K900, L12, L40, L52, L80, L93, M05, M06, M08, M300, M313, M315, M316, M32, M33, M34, M35, M45)	
	Finland	Care register for Health Care, Special Reimbursement Register and Prescription Centre database. Defined as primary or secondary diagnoses (look-back 6 years) or drug prescriptions (look-back 3 years) before 27 December 2020.  *Only if patient also used one of the listed drugs (marked with **)  **Only if patient also had one of the diagnoses (marked with *)	Binary: yes/no (ICD-10 codes: D7081, D7089, D80-D84, E250, E271, E272, E274, E310, E896, D86*, K50*, K51*, L40*, M02*, M05-M07*, M139*, M45*, M460*, M461*, M469*, M941*; ATC-codes**: H02AB02, H02AB04, H02AB06, H02AB07, L01BA01, L01XC02, L04AA06, L04AA10, L04AA13, L04AA18, L04AA24, L04AA26, L04AA29, L04AA33, L04AA37, L04AB, L04AC, L04AA01, L04AD02, L04AX01, L04AX03)	
	Norway	Norwegian Patient Register. Defined as any recorded ICD-10 diagnosis during inpatient or outpatient contact in hospital or from private-practicing specialists and before first Covid-19 vaccination (look-back 3 years).	Binary: yes/no (ICD-10 codes: G35, K50-K51, M05-M09, M13-M14)	

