Length of Covid-19 hospitalisation	Finland	National Care Register for Health Care and the National Infectious Diseases Register. Time between admission and final discharge date.	Categorical (adjustment variable	
	Norway	The Norwegian Intensive Care and Pandemic Registry (NIPaR). Time between admission and final discharge date.	for objective #3 only; 4 levels)e: ≤2 days, 3-5 days, 6-14 days, >14 days	
	Sweden	The Swedish Patient Register and the Register on surveillance of notifiable communicable diseases (SmiNet). Time between admission and final discharge date.		

<sup>a Due to data availability in Sweden, the country-specific end of study period might be some weeks earlier. For the bivalent 4 dose vs monovalent 4 dose comparisons, we will consider whether alternative time period bins should be used for these analyses to optimize the balance between covariate control and matched cohort size. b To account for the risk of severe Covid-19, we will adjust for targeted Covid-19 high-risk groups of severe Covid-19, specifically established for each country. In Denmark, the Covid-19 vaccine priority groups were governmentally assigned and individuals were prioritised according to the risk of severe infection (identified by the treating physicians) as well as whether being health or social care workers. In the remaining countries, the variable was constructed based on the identification of vulnerable individuals (as defined by those receiving nursing care or living in nursing homes) and whether being health or social care workers. c Autoimmunity-related conditions includes a range disorders such as inflammatory bowel diseases, diseases involving the blood, immune mechanism or endocrine systems, inflammatory rheumatic diseases, psoriasis, lupus erythematosus, multiple sclerosis; subject to country-specific definitions. The selected diagnosis codes to define comorbidities were country-specific, based on inputs from national experts and country-specific registration practices as part of the general national surveillance purposes. This was done as we anticipated that

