## 9.7 Data analysis

#### **Procedures**

[figure not shown]
We will use a matched study design to evaluate the effectiveness of a bivalent BA.1 or BA.4-5 (or monovalent [original]) mRNA-booster vaccine (as the fourth dose) in comparison with having received three monovalent vaccine doses only (i.e., nonboosted with a fourth dose) as well as between fourth dose recipients. For the boosted vs nonboosted (i.e., 4 vs 3 dose) comparisons, individuals who have received a fourth dose will be matched on the day of vaccination with individuals who have not yet received a fourth dose. Individuals will be matched on age (5-year bins), calendar time according to when the third dose was received (monthly bins), and a propensity score including sex, region of residence, vaccination priority groups (i.e., individuals at high-risk of severe Covid-19 or healthcare workers), selected comorbidities (chronic pulmonary disease, cardiovascular conditions or diabetes, autoimmunity-related conditions, cancer, and moderate to severe renal disease), and previous history of SARS-CoV-2 infection characteristics. The day the fourth dose was administered within each matched pair will serve as the index date for both individuals. If individuals who were included as a

matched nonboosted (previously three-dose vaccinated) individual (i.e., a reference individual) received a fourth dose later than the assigned index date, they will be allowed to potentially re-enter as a fourth-dose recipient in a new matched pair on that given date. The figure below illustrates the study cohort construction.

For the between booster (i.e., 4 vs 4 dose) comparison, BA.4-5 booster and BA.1 booster recipients (as a fourth dose) will be matched on age (5-year bins), calendar time according to when the fourth dose was received (monthly bins), and a propensity score including sex, region of residence, vaccination priority groups (i.e., individuals at high-risk of severe Covid-19 or healthcare workers), selected comorbidities (chronic pulmonary disease, cardiovascular conditions or diabetes, autoimmunity-related conditions, cancer, and moderate to severe renal disease), and previous history of SARS-CoV-2

infection. The day the fourth dose was administered will serve as the index date for each respective individual. The figure below illustrates the study cohort construction.

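### The main-cohort propensity score omits transplant, nearly all liver-disease codes and, outside Finland, immunodeficiency, although the protocol already defines these flags for objective #4

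*Protocol*

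**What the plan says.** **Who is in the main cohort.** Section 9.2 of the Protocol lists six criteria. None refers to an immunocompromising diagnosis. Two act through dose timing. Criterion 4 reads "Did not receive a booster (i.e., the third or fourth vaccine dose) within 90 days after the last received vaccine dose". Criterion 5 reads "Did not receive the fourth dose before the country-specific start dates (as this would indicate individuals who were particularly vulnerable to severe disease", and goes on to name immunocompromising conditions. Section 9.9 then contrasts the immunocompromised cohort with a general population that it calls immunocompetent.

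**What is adjusted for.** The propensity score in section 9.7 (Procedures) contains sex, region, priority group, previous infection and "selected comorbidities (chronic pulmonary disease, cardiovascular conditions or diabetes, autoimmunity-related conditions, cancer, and moderate to severe renal disease". Age and calendar month of the last shared dose are matched directly. The objective 3 Cox model reuses these covariates, drops previous infection and adds length of stay.

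**Where immunocompromise enters.** Section 9.2 defines five diagnosis-based conditions and one schedule-based condition. For example, the transplant row lists "ICD-10 codes: T86 [except T86.82-T86.84, T86.89, and T86.9" together with "Z94, and Z98.85 registered within 3 years prior to the index date". Section 9.3 uses these as a covariate in one place: "For the immunocompromised cohort analysis (objective #4), we will also include subtype of immunocompromised condition".

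**The concern.** The protocol itself treats immunocompromise as a determinant of when people get a fourth dose (criterion 5) and as a marker of vulnerability to severe disease. A variable of that kind belongs in the adjustment set unless the cohort has been cleared of it. Dose timing clears only part of it: a transplant recipient who took doses on the ordinary schedule, or has not yet taken a fourth, stays in.

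Section 9.9 also says that in the 4 vs 3 contrast the comparator arm is increasingly made up of people who never take a fourth dose as day 365 approaches, and that healthy-vaccinee bias follows if the included covariates do not account for the differences. The covariate list is therefore the stated safeguard for the day-365 primary estimate, and it lacks conditions that the sponsor has already coded for another objective.

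**Working it through.** **Step 1. Compare the code lists.** The section 9.2 definitions were set against the country-specific comorbidity codes in the section 9.3 covariate table.

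| Condition (section 9.2 codes) | Denmark | Finland | Norway | Sweden |
|---|---|---|---|---|
| Transplant (T86, Z94, Z98.85) | no | no | no | no |
| Liver (K70.3, K70.4, K72, K74.3-K74.6, R18) | K743 only | no | no | no |
| Immunodeficiency (D80-D84) | no | yes | no | no |
| Lupus and connective tissue (L93, M32-M35) | yes | no | no | no |
| Multiple sclerosis (G35) | yes | no | yes | yes |
| Dialysis status (Z992) | no | no | no | no |
| Renal failure (N18-N19, renal flag) | yes | yes | yes | yes |
| Solid cancer (C00-C80 without C44) | yes | yes | yes | yes |

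Norway's autoimmunity flag shows how narrow a list can be: "Binary: yes/no (ICD-10 codes: G35, K50-K51, M05-M09, M13-M14".

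**Step 2. Look for a proxy.** In Denmark the priority group reflects risk identified by treating physicians, so it partly covers these patients. In Finland the risk level means people in 24-hour care; in Norway and Sweden it means nursing-home residents. Outside Denmark it is no proxy for transplant, cirrhosis or immunodeficiency in people living at home.

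**Step 3. Size of the possible bias.** For an unadjusted yes/no confounder,

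RR observed = RR true × B, with B = [1 + p1(g − 1)] / [1 + p0(g − 1)].

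Here p1 and p0 are the prevalences of the uncaptured condition in the boosted and unboosted arms after matching, and g is its risk ratio for severe Covid-19. The document gives none of the three, so all are assumptions. The reference VE of 67.8% (RR 0.322) is the BA.4-5 hospitalisation result quoted in section 7. The late VE of 20% (RR 0.80) is assumed.

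- g = 3, p1 = 1%, p0 = 2%: B = 1.02/1.04 = 0.981. 0.322 × 0.981 = 0.316, so VE reads 68.4%. With the arms swapped, B = 1.020 and VE reads 67.2%.
- g = 5, same prevalences: B = 1.04/1.08 = 0.963, VE 69.0%. Swapped, B = 1.038, VE 66.6%.
- Late VE of 20%, g = 5: 0.80 × 0.963 = 0.770, VE 23.0%. Swapped, 0.80 × 1.038 = 0.831, VE 16.9%.
- Milder, g = 3, 2.0% vs 1.5%: B = 1.04/1.03 = 1.010. A VE of 67.8% moves by about 0.3 points.
- Extreme, g = 10, 1% vs 3%: B = 1.09/1.27 = 0.858. VE 67.8% reads 72.4% (62.5% swapped), and VE 20% reads 31.3% (6.8% swapped).

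The shift in VE is (1 − VE) × (1 − B), so the same imbalance costs more points when VE is low.

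**The case against.** **Restriction already removes many of these people.** Criteria 4 and 5 exclude accelerated and early recipients, and in Finland, Norway and Sweden fourth doses for vulnerable people began in spring 2022, before the study period. This stands in part. Only the remainder is at issue, and nothing shows that it takes up a fourth dose at a different rate. But nothing shows the opposite either, and the criteria do not reach people on the ordinary schedule.

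**Dialysis patients.** Because Z992 is unlisted, a reader might infer that the score cannot see them. It largely can: the renal flag carries N18-N19 in every country.

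**Code counts are not patient shares.** Correct. The HIV codes may also be dropped (footnote a to the section 9.2 table). The point rests on whole conditions being absent, not on a tally.

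**Country-specific lists were deliberate.** The notes to the covariate table say that local definitions were expected to identify risk groups better. Footnote c describes the autoimmunity flag as covering "inflammatory rheumatic diseases, psoriasis, lupus erythematosus, multiple sclerosis; subject to country-specific definitions", so missing lupus codes outside Denmark, or G35 in Finland, do not contradict it. This reason does not explain why transplant is absent everywhere.

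**Between-booster comparisons.** Section 9.9 calls the choice of booster type unselective apart from two early weeks in Denmark, and pairs are matched on month of fourth dose. The point is therefore mainly about 4 vs 3.

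**Acknowledged limitation.** Section 9.9 concedes residual unmeasured confounding, and section 9.8 plans matching diagnostics. But these conditions are measured, and the planned diagnostics address the matched parameters, which do not include them.

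**Conclusion.** The gap is real and limited. Transplant is missing from the main score in all four countries, liver disease in all but one code in one country, D80-D84 in three, and L93 and M32-M35 in three. Describing the cohort as immunocompetent rests on dose timing alone. VE *can* be confounded as a result, chiefly in the 4 vs 3 contrast and late in follow-up.

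A reader might go further and conclude that the primary VE *is* confounded. The document does not support that: prevalence, imbalance and risk ratio are all assumed, and the sign can go either way. With prevalences of 1% and 2%, the shift is 0.6 to 1.2 points on a VE of 67.8% for a risk ratio of 3 to 5, and about 3 points on a VE of 20% at a risk ratio of 5.

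Nor does the cohort size show that such a bias would stand clear of sampling error. Precision follows events. Section 9.5 expects at least 2,250 hospitalised four-dose recipients, based on 90-day data. Assume an even split over three boosters (750 each) and a VE of 66%, which implies 750/0.34 ≈ 2,206 comparator events. The standard error of log RR is then √(1/750 + 1/2,206) ≈ 0.042, a 95% interval of about ±8%, against a bias of 2-4% in the RR. Longer follow-up adds events, while matching and random-effects pooling cost precision.

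The change is worth making because it is cheap and replaces an untested assumption with a reported check.

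**What to change.** In sections 9.3 and 9.7:

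1. Add conditions 1-5 of the section 9.2 table as separate yes/no indicators, with the three-year look-back before the index date already defined there, to the propensity score for objectives 1-2 and 5-8. Treat the HIV codes as decided for objective 4.
2. Add the same indicators to the objective 3 Cox model, naming the date from which the look-back runs in that cohort.
3. Report the balance of each indicator after matching.
4. Add one sensitivity analysis of the 4 vs 3 comparison that leaves out everyone with a flag. This also tests the immunocompetent description directly.

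Overlap with the existing cancer and autoimmunity flags does no harm in a propensity score. The indicators also bring in later diagnoses: Finland's comorbidity flags stop at 27 December 2020, and those of Norway and Sweden generally at first Covid-19 vaccination.

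Cost: protocol wording, a few lines in the common R script and a few lost matches. The flags are already to be built for objective 4, so no new data source is needed.

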Received a Covid-19 vaccine dose equivalent of	Either 1) any booster dose (≥3rd dose) within 90 days of the last
booster dose for immunocompromised (6)	dose b , 2) receipt of fourth dose before the roll-out of the 4th dose
	boosters c , or 3) receipt of fifth or more vaccine dose doses prior
	to start of study period

Definitions of immunocompromised condition 1 to 5 are adapted and modified from Embi et al.(12) and Hughes et al.(13) aWe will examine data to determine whether a diagnosis of HIV (ICD-10 codes B20, B21, B22, B231, B232, B24, 0987, Z21) should be included. We do not have access to data on CD4-cell count; if HIV is very rarely occurring (which we assume), we will most likely not include these diagnosis codes in the immunocompromised definition. bCovid-19 vaccination courses in the Nordic countries for the general population has generally had time intervals of 6 months or more between boosters. cOf note, the start date for the roll-out of the fourth dose was earlier than start of the study period in Finland, Norway, and Sweden, as vulnerable and the elderly living in nursing homes were initially prioritized during Spring 2022, before the fourth dose was rolled out to the general population. The exact start date of the roll-out is to be specified in Finland, Norway, and Sweden (approximately February/March 2022), while it coincides with the start of the study period in Denmark (being 1 September 2022).

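### Objective #4: the immunocompromised subtype covariate is described as one six-level variable, but the six conditions can co-occur and three D61 codes sit in two levels, so balance on co-occurring conditions is not assured

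*Protocol*

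**What the plan says.** Entry to the objective #4 cohort (Protocol 9.2) is inclusive: "Immunocompromised will be defined as fulfilling at least 1 of the conditions in the table below". The table has six numbered rows: solid malignancy (1), haematologic malignancy (2), rheumatologic or inflammatory disorder (3), other intrinsic immune condition or immunodeficiency (4), organ or stem cell transplant (5), and a dosing history typical of immunocompromised people (6). Rows 1 to 5 are diagnosis lists read within 3 years before the index date. Row 6 is not a diagnosis. It begins "Either 1) any booster dose (≥3rd dose) within 90 days of the last" and goes on to early fourth doses and to fifth or later doses before the study period.

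Section 9.3 (Covariates) then uses the same six rows for confounder control in this cohort: "we will also include subtype of immunocompromised condition (as categorized in the 6 levels in the table above". No rule is given for a person who meets more than one row.

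Two of the code lists overlap. Row 2 reads "ICD-10 codes: C81-C86, C88, C90-C96, D46, D47, D61.0, D70.0" and continues "D61.2, D61.9, D71 registered within 3 years prior to the index". Row 4 includes "D61, D72.8, D80, D81 [except D81.3], D82-D84, D89 [except", that is, the whole of D61 with no exception for the three subcodes in row 2.

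Section 9.7 applies the main matched design to this cohort: 1:1 matching on age, calendar time and a propensity score.

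**The concern.** A variable with six levels gives each person one value, but the cohort definition lets a person meet two or more rows. Someone with a haematologic malignancy, a stem cell transplant and an early extra dose meets rows 2, 5 and 6. Someone whose only qualifying record is D61.0 already has two values. Any one-value coding must discard something, and for row 6 it discards either the diagnosis or the dosing marker.

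At stake is confounder control for the objective #4 effectiveness estimates. If people with a second condition differ in severe Covid-19 risk, and are unequally represented among boosted and comparator members of the same level, the matching as described does not directly remove that difference. One set of R scripts is run in all four countries (9.6), so whichever coding the programmer picks applies everywhere.

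**Working it through.** The protocol gives no figure on this point, so there is none to reproduce. The check has four parts.

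**1. Is a single variable the natural reading?** In the 9.3 table, levels describe single categorical variables: priority group (3), region (5 or 9 by country), time since infection (3) and length of hospitalisation (4). Where separate indicators are intended, as for the five comorbidities, each is marked as a yes/no variable. The wording for subtype follows the first pattern.

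**2. What can one variable represent?** Six conditions that may co-occur give 2^6 − 1 = 63 non-empty patterns. A mutually exclusive six-level variable has a defined value for 6 of them, leaving 63 − 6 = 57 patterns without a stated level. Six yes/no indicators distinguish all 63.

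**3. Do the code lists overlap?** Expanding the lists for rows 1 to 5 and comparing all 10 pairs shows one overlap: rows 2 and 4, through D61.0, D61.2 and D61.9. Row 4 carves out exceptions for D81, D89 and K74, but none for D61.

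**4. How much do other covariates recover?**
- Cancer is a separate yes/no term, but it does not distinguish solid from haematologic malignancy.
- Autoimmunity-related conditions overlap row 3, to an extent that varies by country. Row 4 is covered only in parts, for example N04 through the renal term and D80–D84 in Finland.
- The row 5 codes (T86, Z94, Z98.85) appear in none of the five comorbidity lists.
- Comorbidities are read before 27 December 2020 in Finland, and before first Covid-19 vaccination in Sweden and for most comorbidities in Norway. Row 1 to 5 diagnoses are read up to the index date. In Finland the study period starts on 18 July 2022, so the gap is at least 568 days (365 to 27 December 2021, plus 203). A condition first diagnosed in that gap enters the score directly only through the subtype variable.

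**Illustration of size (all inputs assumed).** Let a second condition multiply severe Covid-19 risk by R, with prevalence p1 in boosted and p0 in comparators of the same level, and be wholly absent from the score. The spurious risk ratio is (1 + p1(R − 1)) / (1 + p0(R − 1)).

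| p1 / p0 | R = 2 | R = 3 |
|---|---|---|
| 0.20 / 0.15 | 1.20/1.15 = 1.043 | 1.40/1.30 = 1.077 |
| 0.30 / 0.20 | 1.30/1.20 = 1.083 | 1.60/1.40 = 1.143 |

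If the second condition is instead commoner in comparators, the factors invert; the last becomes 1.40/1.60 = 0.875.

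A second grid fixes R = 2 and takes p0 from 0.05 to 0.30 and an odds ratio (OR) between second condition and boosting from 1.0 to 2.0, with p1 = OR·p0 / (1 − p0 + OR·p0). The standardised mean difference (SMD) is (p1 − p0) / √[(p1(1 − p1) + p0(1 − p0))/2].
- p0 = 0.30, OR = 2.0: p1 = 0.462, SMD = 0.337, spurious risk ratio 1.124 (the largest in the grid).
- p0 = 0.30, OR = 1.2: p1 = 0.340, SMD = 0.085, spurious risk ratio 1.030.
- OR = 1.0: SMD = 0, spurious risk ratio 1.000.

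At an OR of 1.2 or less, every SMD in the grid is below 0.1.

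**The case against.** The strongest reply is that section 9.3 nowhere says the levels are mutually exclusive. Six flags would be compatible with the sentence, and a hierarchy is coding detail that an analysis plan or the R scripts could settle. That is fair as far as it goes, and the protocol does not rule out indicators. But its own usage of levels points to one variable, and the D61 double listing is a conflict in this document whatever another document says.

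Subtype is also added to the main covariates rather than replacing them. In the malignancy-plus-transplant example, the malignancy would usually stay in the score through the cancer term. The target trial table in 9.1 makes assignment in this cohort conditional on the number of previous doses, which carries much of row 6. Both points stand and reduce the problem. They do not cover transplant, later-diagnosed conditions in some countries, or the part of row 6 defined by a short dosing interval.

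Matching diagnostics (9.8) and baseline tables before and after matching (section 12) are planned. The diagnostics are aimed at matched parameters, however, and a second condition that was never coded is not one, so they need not reveal its imbalance.

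A reader might infer that patients with several conditions will be poorly balanced, or that they are the most likely to be boosted. The documents support neither: they give no overlap prevalence and no association with boosting. For comparisons between boosters, 9.9 describes the type received as unselective apart from an early Danish prioritisation. A reader might also infer that the D61 overlap affects who enters the cohort. It does not, because either row qualifies.

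**Conclusion.** The point holds in limited form. As described, the subtype covariate does not fit the inclusive cohort definition, and D61.0, D61.2 and D61.9 have two values. On the natural single-variable reading, co-occurring conditions drop out of the propensity score and are only partly recovered by other covariates, so balance on them is not assured. That is weaker than saying balance will be poor.

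Neither the size nor the direction of any bias can be determined from the documents. The factors of 1.04 to 1.14 rest on assumed prevalences and risk multipliers and on the second condition being entirely absent from the score. With a weak association with boosting the effect is negligible. Only secondary objective #4 is affected, and no sample size or power figure changes. This is a low-severity point, worth making because the remedy is nearly free.

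**What to change.** - **9.3 (Covariates):** replace the six-level subtype with six separate yes/no indicators, one per row of the 9.2 table, in the objective #4 propensity score.
- **9.8:** name these six indicators among the variables checked in the matching diagnostics for this cohort.
- **9.2 table:** list D61.0, D61.2 and D61.9 in only one of levels 2 and 4. With indicators the double listing does less harm, but it would still make one diagnosis look like two conditions.

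A stated hierarchy would also give everyone a unique value, but it would still discard the second condition, so indicators are preferable. The cost is a sentence in each of 9.3 and 9.8, one code-list correction and a small change to the common R script. The flags must already be derived to establish eligibility, so no new data are needed.
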